6.6.9 Visit Requirements

Visit requirements are outlined in Section 7.0 - Trial Flow Chart. Specific procedure-related details are provided above in Section 6.0 - Study Procedures.

6.6.9.1 Screening Period

The screening period includes 21 days for pre-study assessments except for scans and consent forms which must be completed within 28 days.

6.6.9.2 Treatment Period

The treatment period consists of up to 34 cycles (2 year) of treatment with pembrolizumab in addition to up to 5 (cohort B) or 6 (cohort A) cycles of chemotherapy. Cohort A and B patients may also have treatment with pembrolizumab interrupted for consolidation thoracic radiation and/or prophylactic cranial irradiation as indicated. Re-treatment after cessation of pembrolizumab following a CR will also continue for up to 1 year (See section 6.6.9.6).

6.6.9.3 Post-treatment visits—Safety Follow-up

For participants who progress on therapy or after completion of therapy, a safety Follow-Up Visit should be conducted approximately 30 days after the last dose of trial treatment or before the initiation of a new anti-cancer treatment, whichever comes first. All AEs that occur prior to the Safety Follow-Up Visit should be recorded. Subjects with an AE of Grade > 1 will be followed until the resolution of the AE to Grade 0-1 or until the beginning of a new anti-neoplastic therapy, whichever occurs first. SAEs that occur within 90 days of the end of treatment or before initiation of a new anti-cancer treatment should also be followed and recorded. Subjects who are eligible for retreatment with pembrolizumab (as described in Section 6.6.9.6) may have up to two safety follow-up visits, one after the Treatment Period and one after the Second Course Phase.

6.6.9.4 Post-treatment visits—Follow up Visits

Subjects who discontinue trial treatment for a reason other than disease progression will move into the Follow-Up Phase and should be assessed every 6 weeks (42 ± 7 days) by radiologic imaging to monitor disease status. After 27 months (the maximum time of treatment + 3 months), the imaging time point will occur every 12 weeks (± 7 days). Every effort should be made to collect information regarding disease status until the start of new anti-neoplastic therapy, disease progression, death, end of the study or if the subject begins retreatment with pembrolizumab as detailed in Section 6.6.9.5 Information regarding post-study anti-neoplastic treatment will be collected if new treatment is initiated.

Subjects who are eligible to receive retreatment with pembrolizumab according to the criteria in Section 6.6.9.6 will move from the follow-up phase to the Second Course Phase when they experience disease progression. Participants treated in the second course phase should follow the schedule of assessments as for maintenance pembrolizumab cycles in section 7.0.

CONFIDENTIAL

6.6.9.5 Survival Follow-up

Once a subject experiences confirmed disease progression or starts a new anti-cancer therapy, the subject moves into the survival follow-up phase and should be contacted by telephone every 12 weeks to assess for survival status until death, withdrawal of consent, or the end of the study, whichever occurs first.

6.6.9.6 Second Course Phase (Retreatment Period)

Subjects who stop pembrolizumab with SD or better may be eligible for up to one year of additional pembrolizumab therapy if they progress after stopping study treatment. This retreatment is termed the Second Course Phase of this study and is only available if the study remains open and the subject meets the following conditions:

- **Either**

- Stopped initial treatment with pembrolizumab after attaining an investigator-determined confirmed CR according to RECIST 1.1, and
 - Was treated for at least 24 weeks with pembrolizumab before discontinuing therapy
 - Received at least two treatments with pembrolizumab beyond the date when the initial CR was declared

OR

- Had SD, PR or CR and stopped pembrolizumab treatment after 12 months of study therapy for reasons other than disease progression or intolerability

AND

- Experienced an investigator-determined confirmed radiographic disease progression after stopping their initial treatment with pembrolizumab
- Did not receive any anti-cancer treatment since the last dose of pembrolizumab
- Has a performance status of 0 or 1 on the ECOG Performance Scale
- Demonstrates adequate organ function as detailed in Section 4.1.9
- Female subject of childbearing potential should have a negative serum or urine pregnancy test within 72 hours prior to receiving retreatment with study medication.
- Female subject of childbearing potential should be willing to use 2 methods of birth control or be surgically sterile, or abstain from heterosexual activity for the course of the study through 120 days after the last dose of study medication (Reference Section 5.10.2). Subjects of child bearing potential are those who have not been surgically sterilized or have been free from menses for > 1 year.
- Male subject should agree to use an adequate method of contraception starting with the first dose of study therapy through 120 days after the last dose of study therapy.
- Does not have a history or current evidence of any condition, therapy, or laboratory abnormality that might interfere with the subject's participation for the full duration of the trial or is not in the best interest of the subject to participate, in the opinion of the treating investigator.

Subjects who restart treatment will be retreated at the same dose and dose interval as when they last received pembrolizumab. Treatment will be administered for up to one additional year. Visit requirements will be the SAME as those for all cycles of maintenance pembrolizumab as outlined in Study Calendar/Protocol Flow Chart in section 7.

6.7 Biomarker, Correlative, and Special Studies

6.7.1 Biomarker/Correlative Studies

The studies described below are all ancillary/exploratory in nature and are designed to determine whether protein expression, mutational burden, gene expression, soluble PD-L1 or immune cell profiling can be associated with clinical benefit or resistance.

6.7.1.1 Immunohistochemistry

PD-L1 has been studied extensively in studies of pembrolizumab and other PD-1/PD-L1 inhibitors with mixed results, although this has been attributed to variability in different assays and in different definitions of positivity.

There is less data on whether PD-L1 positivity is common in other thoracic malignancies such as small cell lung cancer (SCLC) and it is thought that the rate of positivity may be lower in SCLC, although this determination is based primarily archival tissue evaluation primarily from surgical resections²⁶. There is some data that immune infiltrate may be more prevalent in SCLC and the relative importance of PD-L1 expression in each of these compartments remains to be determined for SCLC. A recent basket study of pembrolizumab which included SCLC patients found a 28.6% rate of positivity of PD-L1 (on at least 1% of tumor cells) from archival specimens²¹.

SCLC is also unique compared to both NSCLC and melanoma in that it demonstrates robust response rates to both chemotherapy and radiation, both of which could modulate PD-L1 expression. Therefore, PD-L1 expression and the degree of immune infiltrate could change in response to therapy and influence the effectiveness of anti-PD-1 therapy.

This study will evaluate cohorts of patients receiving pembrolizumab prior to any therapy (cohort A), after 1-2 cycles of chemotherapy (cohort B), after completion of 1st line chemotherapy (cohort C), and after completion of radiotherapy (cohort D) to evaluate changes in PD-L1 expression as assessed by immunohistochemistry compared to pre-treatment samples. In addition, CD3 immunostaining will be performed to evaluate the degree of immune infiltrate in tumor specimens pre- and post- chemotherapy or radiotherapy.

Finally, other markers of immune suppression will be simultaneously evaluated in all specimens. [name] of NYU has developed a quantitative immunofluorescence platform that can simultaneously measure up to 7 markers. This assay is currently being optimized on lung cancer specimens and will be used as the methodology of evaluation in this study. The current optimized markers are PD-1, PD-L1, CD3, CD8, CD163, and IDO1. PD-L1 IHC will also independently be done at NYU using the 22C3 antibody optimized on a Ventana Platform as per Neuman T et al, Journal of Thoracic Oncology 2016.

6.7.1.2 Collection of Specimens

For cohort Archival tissue from a biopsy obtained within six weeks of study start (minimum 20 5 um slides, 25 preferred) will be required (this sample could be archival tissue from a diagnostic biopsy although if insufficient material is available, a fresh tissue biopsy should be obtained). For cohorts B-D, an archival (diagnostic) tissue biopsy (minimum 20 5 um slides, 25 preferred) will be required (prior to initiation of any treatment). In addition, for cohorts B-D, a *new* core tissue biopsy (minimum 3 cores from lung tissue, minimum 4 cores from any other site) will be required prior to study entry. All biopsies will be performed at individual sites where participants are enrolled.

A minimum of 4 participants in each cohort (B-D) will be required to have fresh tissue sampling from which FNA will be also obtained (in addition to core biopsies) for immune profiling at the Belfer Institute. For those participants, FNA will be immediately placed into RPMI media and hand-couriered to the Belfer Institute ([name]) or to the [name] laboratory at NYU (identical SOP's for immunophenotyping exist at both institutions. for processing. The remaining core biopsies will be formalin-fixed and paraffin-embedded as per institutional standards for further evaluation with IHC or tumor DNA/RNA extraction for sequencing or nanostring and shipped to the Overall PI, [name] (see also Section 6.7.2.1).

Optional core biopsies will be obtained at the time of tumor progression from participants who consent to this procedure. A minimum of 3 cores will be required.

A block or minimum of 20 5 um slides (formalin-fixed, paraffin embedded (FFPE)), (25 preferred) will be requested from both archival (diagnostic) biopsy specimens and pre-treatment biopsy specimens.

6.7.1.3 Collection of Specimen, Handling, Shipping, sites performing IHC

Specimens will be collected by the clinical research coordinator (CRC) from each participating site and shipped directly to the coordinating CRC at DFCI at room temperature (5-10 5 um slides). Immunostaining will be performed at the DF/HCC Histopathology core facility (located in the Brigham and Women's Hospital) under the direction of [name] with interpretation by [name] or his delegate.

Samples should be shipped at ambient temperature to the following address:

NYU Center for Biospecimen Research and Development (CBRD)

Alexandria Center for Life Science

[name]

[name]

CBRD [contact]

[contact]

[contact]

6.7.2 DNA sequencing

Neoantigen load has been proposed as an important biomarker of potential sensitivity to PD-1 and PD-L1 inhibition in multiple tumor types²⁸, and compared to other malignancies, small cell lung cancer has a high mutational burden due to the very high association with heavy smoking. Given the reported lower level of PD-L1 expression in SCLC, mutational burden may be a relatively more important biomarker in this setting.

We will plan to conduct whole-exome sequencing on a subset of patients in collaboration with [name] and [name] [name] of the Broad Institute.

6.7.2.1 Collection of Specimens

7-10 5 um slides (formalin-fixed, paraffin embedded (FFPE)) from both archival (diagnostic) biopsy specimens and pre-treatment biopsy specimens will be used to isolate tumor DNA in the Center for Advanced Molecular Diagnostics (CAMD) at BWH. A subset of samples (those from which we have the most tissue, up to 20 total) will be subjected to both whole-exome sequencing (WES) in collaboration with [name] at the Broad Institute

Samples should be sent at ambient temperature to the overall study PI at the below address; so that we can determine feasibility of sequencing with [name] of pathology (NYU) and then distribute samples accordingly (to the Broad Institute, BWH path, and BWH molecular path):

NYU Center for Biospecimen Research and Development (CBRD)

Alexandria Center for Life Science

[name]

[name]

CBRD [contact]
[contact]
[contact]

6.7.2.2 Collection of Specimen, Handling, Shipping, site performing sequencing

Specimens will be collected by the clinical research coordinator (CRC) from each participating site and shipped directly to the coordinating CRC at NYU at room temperature.

WES will be performed at the Broad Institute under the direction of [name] [name] on a subset of specimens (20 tissue and 20 blood). Whole-exome sequencing will be performed at the Broad Institute in accordance with IRB sanctioned practices involving Protected Health Information (PHI). De-identified data will be maintained on a secure server and the results of these research tests will not be shared with study subjects.

6.7.3 Gene Expression

Inflammatory or immune-related gene expression signatures have been suggested to serve as predictors of clinical benefit beyond PD-L1 expression in multiple tumor types treated with pembrolizumab^{29,30} and will be evaluated in a subset of pre-treatment biopsies (20) on this study. Tumor-derived RNA from 5-8 5 um slides will be used for Nanostring using the nCounter Human PanCancer Immune Profiling kit, to be performed in the DF/HCC genomics core facility. Interpretation/analysis will be performed in collaboration with [name] on a subset of specimens (20).

6.7.4 Immune profiling

Immune profiling in tumor biopsies is actively under evaluation at the Belfer Center for Applied Cancer Science at DFCI and at the [name] laboratory at NYU to understand correlates of response and resistance. Preliminary data has been generated in both mesothelioma and NSCLC and we are currently generating data from SCLC samples as well. To date, data in other tumor types has suggested that the best cell collection is obtained from FNA samples.

6.7.5 Blood biomarkers

Soluble PD-L1 analysis from peripheral blood samples has been extensively studied in melanoma in [name]'s lab at DFCI and is now being evaluated in all tumor types under the Center for Immuno-Oncology core facility. Blood may also be used for the evaluation of cytokine profiles and exosomal profiling as these assays are developed. Finally, in order to evaluate genomic changes (particularly with regard to neoantigen profile) that may occur as a result of exposure to chemotherapy and radiation, in addition to evaluating tissue samples pre/post therapy, we will also collect blood for evaluation of circulating free DNA and for samples where there is adequate DNA pre and post therapy, we will subject a subset of these samples (up to 15) to whole-exome sequencing for evaluation of genomic change and neontigen profile change. A sample of whole blood for germline comparison will also be collected.

6.7.5.1 Collection, Handling, Shipping, and Site Performing analyses for circulating markers

Blood samples for potential cytokine, cell profiling, and soluble PD-L1 analysis will be drawn at the time of venipuncture during routine clinic visits. 10-20 ml blood (minimum of 10 ml) will be drawn into EDTA-containing tubes, and plasma will be separated from the cellular component by centrifugation over Ficoll. The separated PBMCs will be allocated into plastic freezing tubes, catalogued, and frozen at -70°C in 10% DMSO using standard methods available for future assays. Note: the period from draw to freezing of samples must be less than 3 hours.

Samples should be shipped on dry ice to:

NYU Center for Biospecimen Research and Development (CBRD)
Alexandria Center for Life Science
[name]
[name]
CBRD [contact]
[contact]
[contact]

6.7.5.2 Collection, Handling, Shipping, and Site Performing analyses for circulating free DNA

For cf DNA samples, blood will be collected in 10 cc EDTA tubes, barcoded, and processed within 3 hours of blood draw. We have previously confirmed that white blood cells remain stable during this period of time and thus, do not affect the purity of tumor-derived cell-free DNA. 1mL of whole blood will be banked from each tube and frozen at -80C in a 2d-barcoded tube until further processing. The remaining blood will be subjected to two rounds of centrifugation (2,000 x g for 10 min followed by 15,000 x g for 10min). Plasma will be removed and frozen at -80C in another 2d-barcoded tube until further processing. All samples are registered in our laboratory information management system and tracked throughout the process. Extractions of cell-free DNA and germline DNA will be performed from banked plasma and whole blood, respectively, using an automated liquid handler. Liquid handling systems will also be used for the subsequent steps of quantification, normalization, and library construction. Sequencing on the Illumina HiSeq will be used to assess the purity of tumor-derived cell-free DNA. Samples with sufficient purity of tumor-derived cell-free DNA will be nominated for hybrid capture of the entire human exome and sequenced on the Illumina HiSeq.

Samples should be shipped on dry ice to:

The Broad Institute
Attn: Blood Biopsy Group
[name]
Lab 4045
[name]

7 Study Calendar/Protocol Flow Chart

Baseline evaluations are to be conducted within 21 days prior to start of protocol therapy. Scans and x-rays must be done ≤ 28 days prior to the start of therapy.

Assessments must be performed prior to administration of any study agent. Study assessments and agents should be administered within ± 3 days of the protocol-specified date, unless otherwise noted.

Study Calendar/Protocol Flow Chart Cohort A and B

	Screening (days --28 to 0)	C1 ^a	C2	C3-6 ^b	Maintenance Pembro ^c C1-34	End of Treatment	Post-Treatment			Second Course phase (Retreatment)
							Safety Follow-up	Follow-up	Survival follow-up	
Pembrolizumab		A	A	A	A		Safety Follow-up	Follow-up	Survival follow-up	A
Cisplatin or Carboplatin ¹		B	B	B						
Etoposide ²		C	C	C						
Informed consent	X									X ^h
Demographics	X									
Medical history	X									X
Concurrent meds	X	X	X	X	X	X				X
Details of prior therapy for cohort B	X									
Physical exam	X	X	X	X	X	X		X ^g		X
Vital signs	X	X	X	X	X	X		X ^g		X
Height	X	X	X	X	X	X				X
Weight	X	X		X	X	X				X
Performance status	X	X		X	X	X		X ^g		X
CBC w/diff, plts ^d	X	X	X	X	X	X		X ^g		X
Serum chemistry ^e	X	X	X	X	X	X		X ^g		X
EKG	X									
Adverse event evaluation	X	X	X	X	X	X	X	X ^g	X ⁱ	X
Tumor measurements/radiologic evaluation ^f	X			X	X	X		X ^g		X
Pulmonary Function Tests	X									
B-HCG	X ^e									X ^e
Tumor (archival) biopsy ⁱ	X									
Tumor biopsy (pre-treatment) ^j	X									
Tumor biopsy (post-treatment), optional						X ^h				
Blood samples for correlative studies		X ^k	X ^k		X ^k	X ^k				X ^k

^aPembrolizumab will be given on day 1 of each cycle. Carboplatin or cisplatin will be given on day 1 of each cycle. Etoposide will be given on days 1, 2, and 3 of each cycle.

^bCohort A participants will be treated with combination chemotherapy + pembrolizumab for a minimum of 4 and a maximum of 6 cycles. Cohort B participants will be treated for a minimum of 3 and a maximum of 5 cycles of combination therapy if they had only one cycle prior to study and a minimum of 2 or maximum of 4 if they had 2 cycles of therapy prior to study.

^cContinued maintenance pembrolizumab will be given on day 1 of each cycle after completion of chemotherapy with 1st dose 3 weeks after last cycle day 1 up through a maximum of 17 cycles following completion of chemotherapy. Interruption of therapy for planned radiation may occur as detailed in sections 5.5.5.1 and 5.11.1

^dSee Table 5 for details.

^eSee Table 5. BHCG, Free T4, T3, PT/PTT, uric acid will be drawn at screening only and thereafter as clinically indicated.

^fRadiologic assessment should include chest/abdomen/pelvis CT scan at baseline following by CT scan or MRI as appropriate to follow known areas of disease. Participants who have untreated brain metastases should have brain MRI at every scheduled radiologic assessment. For participants who DO NOT have baseline brain metastases, brain MRI should be performed on the planned radiologic assessment after completion of chemotherapy. For participants who do not have brain metastases after completion of chemotherapy and DO NOT undergo prophylactic cranial irradiation, brain MRI should be performed every 12 weeks following the completion of chemotherapy. Other radiologic assessments should occur every 6 weeks (within 7 days prior to every other cycle—prior to cycle 3, 5, 7, 9, etc).

^gIn the follow-up phase, exam, VS, laboratory assessments, and radiologic assessments should occur every 6 weeks for up to 18 weeks and then every 12 weeks thereafter.

^hParticipants who proceed to second course phase of treatment (re-treatment after progression with no intervening therapy) should sign consent for second-course phase and meet eligibility requirements prior to initiation of treatment. During treatment, assessments (laboratory, radiographic, blood collection) should follow schedule of maintenance pembrolizumab cycles. At the time of SECOND PROGRESSION, end-of-treatment, safety follow-up, and survival follow-up assessments should be as for 1st progression.

ⁱArchival biopsy with adequate tissue REQUIRED prior to starting on study (minimum 20 5 um slides)

^jPre-treatment biopsies should be fresh biopsies for at minimum 4 participants in each cohort. For these participants, FNA in addition to core-needle biopsy (minimum 3-4 cores—see section 6.6.7.1 for specific requirements. For all participants, biopsies should be within 4 weeks of starting treatment with pembrolizumab and AFTER the last dose of prior therapy.

^kBlood samples will be drawn at the time of venipuncture during routine clinic visits. See section 6.7.4 for details.

^lSafety-follow up evaluation should occur within 30 days of end of treatment.

Study Calendar/Protocol Flow Chart For Cohorts C and D

	Screening (days – 28 to 0)	Maintenance Pembro C1-34	End of Treatment	Post-Treatment			Second Course phase (Retreatment)
				Safety Follow-up	Follow-up	Survival follow-up	
Pembrolizumab ^a		A					A
Informed consent	X						X ^f
Demographics	X						
Medical history	X						X
Concurrent meds	X	X	X				X
Details of prior therapy and response	X						
Physical exam	X	X	X		X ^g		X
Vital signs	X	X	X		X ^g		X
Height	X	X	X				X
Weight	X	X	X				X
Performance status	X	X	X		X ^g		X
CBC w/diff, plts ^b	X	X			X ^g		X
Serum chemistry ^c	X	X			X ^g		X

EKG	X						
Pulmonary Function Tests	X						
Adverse event evaluation	X	X	X	X	X ^g	X ^l	X
Tumor measurements/radiologic evaluation ^d	X	X	X		X ^e		X
B-HCG	X ^c						X ^e
Tumor biopsy (archival) ^g	X						
Tumor biopsy (pre-treatment) ^h	X						
Tumor biopsy (post-treatment), optional			X ^h				
Blood samples for correlative studies		X ^k	X ^k				X ^k

^aPembrolizumab will be given on day 1 of each cycle. Dosing may be interrupted for planned or palliative radiation as per section 5.5.5.1 and 5.11.1

^bSee Table 5 for details.

^cSee Table 5. Free T4, T3, PT/PTT, uric acid will be drawn at screening only and thereafter as clinically indicated.¹

^dRadiologic assessment should include chest/abdomen/pelvis CT scan at baseline following by CT scan or MRI as appropriate to follow known areas of disease. For participants in cohort C (who do not have brain metastases after completion of chemotherapy and DO NOT undergo prophylactic cranial irradiation) brain MRI should be performed every 12 weeks following the completion of chemotherapy. Other radiologic assessments should occur every 6 weeks (within 7 days prior to every other cycle—prior to cycle 3, 5, 7, 9, etc).

^eIn the follow-up phase, exam, VS, laboratory assessments, and radiologic assessments should occur every 6 weeks for up to 18 weeks and then every 12 weeks thereafter.

^fParticipants who proceed to second course phase of treatment (re-treatment after progression with no intervening therapy) should sign consent for second-course phase and meet eligibility requirements prior to initiation of treatment. During treatment, assessments (laboratory, radiographic, blood collection) should follow schedule of maintenance pembrolizumab cycles. At the time of SECOND PROGRESSION, end-of-treatment, safety follow-up, and survival follow-up assessments should be as for 1st progression.

^gArchival biopsy with adequate tissue REQUIRED prior to starting on study (minimum 20 5 um slides)

^hParticipants who proceed to second course phase of treatment (re-treatment after progression with no intervening therapy) should sign consent for second-course phase and meet eligibility requirements prior to initiation of treatment. During treatment, assessments (laboratory, radiographic, blood collection) should follow schedule of maintenance pembrolizumab cycles. At the time of SECOND PROGRESSION, end-of-treatment, safety follow-up, and survival follow-up assessments should be as for 1st progression.

^jPre-treatment biopsies should be fresh biopsies for at minimum 4 participants in each cohort. For these participants, FNA in addition to core-needle biopsy (minimum 3-4 cores—see section 6.6.7.1 for specific requirements. For all participants, biopsies should be within 4 weeks of starting treatment with pembrolizumab and AFTER the last dose of prior therapy.

^kBlood samples will be drawn at the time of venipuncture during routine clinic visits. See section 6.7.4 for details.

^lSafety-follow up evaluation should occur within 30 days of end of treatment.

8 Measurement of Effect

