5.3 Treatment Regimen

Pembrolizumab will be administered every 3 weeks, with 21 consecutive days defined as a treatment cycle. For cohort A, pembrolizumab will be administered together with ALL cycles of chemotherapy (4-6 total cycles). For cohort B, pembrolizumab will be administered together with cycles during study which may be 3-5 additional cycles. Specifically, participants in cohort B should have received 1 prior cycle of chemotherapy. These patients should be continued on the same treatment regimen while on

study to a TOTAL of 3-5 cycles of chemotherapy (on and off study). For cohorts C and D, pembrolizumab will be administered as monotherapy (see below).

Cisplatin (75 mg/m²) or carboplatin (AUC 6) will be administered every 3 weeks, with 21 consecutive days defined as a treatment cycle. Either cisplatin or carboplatin will be administered together with etoposide 100 mg/m² given on days 1, 2, and 3 as per institutional standards of care. Criteria for treatment and dose modifications for each of these drugs will occur as per institutional standards of care.

Platinum and etoposide treatments will be given only in cohorts A and B. Cohorts C and D will have pembrolizumab monotherapy following completion of standard therapy.

Cohort A: pembrolizumab + carboplatin or cisplatin + etoposide X 4-6 cycles followed by pembrolizumab monotherapy for up to 2 year (34 cycles post-combination therapy).

Cohort B: Participants may have received 1 cycle of prior therapy. They will be continued on the SAME treatment regimen (carboplatin or cisplatin + etoposide) together with pembrolizumab for up to a TOTAL of 4-6 cycles (including cycles prior to study). Treatment with the combination should start no sooner than 3 weeks and no later than 5 weeks from the start of the last cycle of chemotherapy. Maintenance pembrolizumab will continue following completion of combination therapy for up to 2 years (34 cycles post-combination therapy).

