FOR COHORTS A AND B ONLY: Initial enrollment will include only 3 participants, who may be enrolled into either cohort A or B. Once these three participants have cleared cycle 1, an additional 3 participants may be enrolled into either cohort A or B if no DLTs are seen. If < 2 DLTs are seen in the first 6 participants, enrollment to the rest of the cohorts will proceed. If ≥ 2 DLTs are seen, enrollment will be halted and discussion of dosing change with Merck and the overall PI will occur prior to further enrollment. Based on safety data to date with other platinum-based regimens, we do not anticipate interactions that would necessitate dosing change, so there will not be pre-specified dose reductions planned. Cohorts A and B will be pooled for the purposes of DLT evaluation as the treatment regimen after study initiation is identical.

Cohort C: participants will have previously received 4-6 cycles of platinum-based therapy and have stable disease. In addition, these patients must not be candidates for further consolidation thoracic radiotherapy or PCI. Pembrolizumab treatment should start no sooner than 2 weeks and no later than 6 weeks from the start of the last cycle of chemotherapy. Therapy will continue for up to 34 cycles (2 years).

Cohort D: participants will have previously received 4-6 cycles of platinum-based chemotherapy and thoracic radiation therapy or PCI or both. Pembrolizumab treatment should start no sooner than 2 weeks and no later than 6 weeks from the start of the last dose of radiation. Therapy will continue for up to 34 cycles (2 years).

Treatment will be administered on an outpatient basis. Reported adverse events and potential risks are described in Section 1.8.1. Appropriate dose modifications are described in Section 5. No investigational or commercial agents or therapies other than those described below may be administered with the intent to treat the participant's malignancy.

All patients will be required to have a tissue biopsy within 3 weeks of study entry and after completion of prior therapy (see section 6.6.7.1). For cohort A, this time frame could be up to 6 weeks.

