5.5 Agent Administration

5.5.1 Pembrolizumab

Pembrolizumab 200 mg will be administered as a 30 minute IV infusion on day 1 of every 21 day cycle.

After completion of chemotherapy, pembrolizumab will be administered as monotherapy for up to a total of 34 cycles (2 years of monotherapy).

Sites should make every effort to target infusion timing to be as close to 30 minutes as possible. However, given the variability of infusion pumps from site to site, a window of -5 minutes and +10 minutes is permitted (i.e., infusion time is 30 minutes: -5 min/+10 min).

The Pharmacy Manual for pembrolizumab contains specific instructions for the preparation of the pembrolizumab infusion fluid and administration of infusion solution.

5.5.2 Cisplatin or carboplatin and etoposide.

Cisplatin, carboplatin, and etoposide should be administered as per institutional standards.

Cisplatin 75 mg/m² will be administered as an IV infusion per institutional standards on day 1 of every 21 day cycle for up to 6 cycles for cohort A and for up to 5 cycles for cohort B (total number of cycles of chemotherapy on and off study should not total more than 6)

Carboplatin AUC 6 will be administered as an IV infusion per institutional standards on day 1 of every 21 day cycle for up to 6 cycles for cohort A and for up to 5 cycles for cohort B (total number of cycles of chemotherapy on and off study should not total more than 6)

Etoposide 100 mg/m² will be administered as an IV infusion per institutional standards on day 1, day 2, and day 3 of every 21 day cycle for up to 6 cycles for cohort A and for up to 5 cycles for cohort B (total number of cycles of chemotherapy on and off study should not total more than 6).

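### The cohort A/B study calendar caps maintenance pembrolizumab at 17 cycles in footnote c, but its own column and sections 5.3, 5.5.1 and 6.6.9.2 give 34

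*Combined protocol and SAP*

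**What the plan says.** Footnote c to the cohort A/B calendar in section 7 starts maintenance three weeks after day 1 of the last chemotherapy cycle and lets it run "up through a maximum of 17 cycles following completion of chemotherapy". The footnote is attached to the column headed "Maintenance Pembro ^c C1-34".

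The body of the protocol states the limit for these cohorts in three places:

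- Section 5.3, cohort A: combination therapy is "followed by pembrolizumab monotherapy for up to 2 year (34 cycles post-combination therapy)".
- Section 5.3, cohort B: "Maintenance pembrolizumab will continue following completion of combination therapy for up to 2 years (34 cycles post-combination therapy)".
- Section 5.5.1: once chemotherapy is complete, "pembrolizumab will be administered as monotherapy for up to a total of 34 cycles (2 years of monotherapy)".
- Section 6.6.9.2: the treatment period is "up to 34 cycles (2 year) of treatment with pembrolizumab in addition to up to 5 (cohort B) or 6 (cohort A) cycles" of chemotherapy.

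For cohorts C and D, which receive pembrolizumab alone from study entry, section 5.3 says "Therapy will continue for up to 34 cycles (2 years)". Section 5.9 also gives 34 cycles or two years, without saying where the count begins.

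**The concern.** Footnote c and the column it annotates describe the same doses, counted from the same point, and they differ by a factor of two. This is a dosing limit in the table that sites use to schedule visits, in a trial that provides for several sites. Nothing in the protocol says which figure prevails.

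What is at stake is treatment duration for participants in A and B who have not progressed about a year into maintenance. One site could stop them while another keeps treating. Read literally, the footnote also gives the cohorts that start pembrolizumab earliest in the disease course fewer total doses than the cohorts that start it last, and the protocol offers no reason for that.

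**Working it through.** **Inputs.** Cycle length is 21 days (section 5.3). The maintenance cap is 17 cycles in footnote c, and 34 in the calendar column and in sections 5.3, 5.5.1 and 6.6.9.2. Combination cycles on study are 4–6 in cohort A and 3–5 in cohort B (section 5.2, Table 2 footnote). The cap for C and D is 34 cycles (section 5.3).

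**Step 1: does 34 match the stated two years?**

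- 34 × 3 weeks = 102 weeks; 34 × 21 = 714 days; 714 / 365.25 = 1.95 years.
- In the other direction, 730.5 / 21 = 34.8, so 34 full cycles fit in two years. The protocol's figure is reproduced.

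**Step 2: does 17?**

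- 17 × 3 = 51 weeks; 17 × 21 = 357 days; 357 / 365.25 = 0.98 years. It does not.

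**Step 3: could 17 come from a different starting point?** Suppose the 34 cycles included the combination cycles. Maintenance would then be:

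- cohort A: 34 − 6 to 34 − 4 = 28 to 30 cycles;
- cohort B: 34 − 5 to 34 − 3 = 29 to 31 cycles.

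Neither range is near 17.

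**Step 4: maximum pembrolizumab doses per participant.**

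| Cohort | Footnote c | Section 5.3 |
|---|---|---|
| A | (4 to 6) + 17 = 21–23 | (4 to 6) + 34 = 38–40 |
| B | (3 to 5) + 17 = 20–22 | (3 to 5) + 34 = 37–39 |
| C, D | not applicable | 34 |

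**Step 5: when the two limits part.** With no dose interruptions, the first dose that section 5.3 allows and footnote c withholds falls at:

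- cohort A: (21 to 23) × 3 = week 63 to 69;
- cohort B: (20 to 22) × 3 = week 60 to 66.

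The gap between the limits is (34 − 17) × 3 = 51 weeks.

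**Step 6: compare with the named measures.** Sections 2.2 and 3.3 name progression-free survival at 3 and 6 months, overall survival at 6 months, response at 6 and 12 weeks, and medians set against historical values of 5.4 and 9.5 months. At 365.25 / 12 / 7 = 4.348 weeks per month, 6 months is 26 weeks, 5.4 months is 23 weeks and 9.5 months is 41 weeks. All come before week 60.

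**The case against.** The best defence is that a careful reader is unlikely to be misled. The figure 34 stands in the very heading that carries the footnote, and the body text repeats it, so a site would meet the conflict at once and has consistent text to follow. That limits the practical risk. It does not remove the error, because no wording reconciles the two figures and the footnote is the more specific instruction.

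A second objection is that the replacement number depends on whether the two-year limit counts from the first pembrolizumab dose or from the end of combination. The ambiguity is real. Section 4.6.2 speaks of 24 months of pembrolizumab, section 6.6.9.4 treats 27 months as the maximum plus three, and item 3 of the opening summary (Treatment Plan) refers to two years in total while also mentioning completion of standard treatment. But it is a separate question. Neither origin gives 17, and the passages that state an origin explicitly, in sections 5.3 and 5.5.1, count after combination or chemotherapy. The retreatment year is no explanation either: it has its own calendar column, and footnote c counts from the end of chemotherapy.

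Two stronger readings are tempting. A reader might infer that 17 cycles, being close to a year, is left over from a one-year plan, and that the retreatment criterion in section 6.6.9.6, for those who "stopped pembrolizumab treatment after 12 months of study therapy for reasons other than disease progression", is an error of the same origin. The documents do not support this. That criterion is an eligibility threshold for retreatment, not a dosing cap, and a participant who completes 24 months under section 4.6.2 also satisfies it. A reader might also infer that the efficacy results are compromised. Step 6 shows why that goes too far.

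**Conclusion.** Footnote c is wrong as written. Its 17 cycles contradict the column it annotates and sections 5.3, 5.5.1 and 6.6.9.2, and no counting origin rescues it.

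The size is up to 17 cycles, or 51 weeks, of maintenance withheld from an A/B participant who has not progressed. The lower total-dose ceiling relative to C and D follows from the same slip and is not a second defect.

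The dose totals assume 3–5 on-study combination cycles in cohort B, as Table 2 states. The week numbers assume no interruptions; the planned radiation breaks in A and B would move the divergence later. How many participants would still be on drug by then cannot be derived from the documents, and the conclusion does not need that number.

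The PD-L1 primary endpoint, the sample size and the power statement do not depend on maintenance duration. The fixed early measures are complete before the limits diverge. The medians would be touched only if they fell well beyond the historical values. This is worth correcting in the next amendment but does not threaten the analysis.

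**What to change.** In footnote c of the cohort A/B calendar, change 17 to 34. This matches the column heading and the explicit post-combination wording in sections 5.3 and 5.5.1.

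Optionally, in the same amendment, state once that the 34-cycle, two-year limit counts from the end of combination therapy in cohorts A and B. Then align the places that leave this open or suggest otherwise: items 3 (Treatment Plan) and 5 (Treatment Regimen) of the opening summary, section 4.6.2, the Table 2 footnote in section 5.2 and its copy in the Appendix B pharmacy manual, section 5.9, and section 6.6.9.4. The 27-month imaging switch in section 6.6.9.4 rests on a 24-month maximum (27 − 3) and would need recalculating. With 40 doses in cohort A, treatment could last 40 × 3 = 120 weeks, or 120 / 4.348 = 27.6 months.

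The 12-month criterion in section 6.6.9.6 needs no change on this account. The cost is amendment wording, with no change to sample size, endpoints or analysis.
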